8.10 Physical Examination

Complete physical examination

A complete physical examination (excluding breast, genital, and rectal examinations) will be performed at SCR. The examination includes a review of major organ systems as well as body height and weight. The examination should be directed at finding evidence of any infections, tumors and lymphadenopathy (a grading scale for lymphadenopathy is included in [Appendix 2](#)). In addition, auscultation of the heart and lungs will be performed to check specifically for signs of any heart condition or respiratory disorders.

Any clinically significant findings at the baseline physical examination will be recorded as medical history events. The only data captured in the eCRF for the physical examination itself will be the date it was performed. Any new or worsening clinically significant findings post-treatment will be captured as AEs.

Targeted physical examination

A targeted physical examination, guided by any signs or symptoms previously identified or any new symptoms that the subject has experienced since the last visit, is required according to the trial schedule ([Section 1.4](#)). In addition, auscultation of the heart and lungs will be performed to check specifically for signs of any heart condition.

Clinically significant findings from the active trial phase physical examinations will be recorded as AEs.

8.11 Vital Signs

At SCR and every other trial visit as defined in the trial schedule ([Section 1.4](#)), blood pressure and pulse rate will be taken after the subject has been sitting upright for approximately 2 minutes. Body temperature will be measured orally. Height and weight will be collected at SCR.

8.12 Unsolicited AEs

All intercurrent diseases reported when the investigator actively inquires the subject will be documented and all required details (e.g., start and stop date, intensity) will be assessed. Unsolicited AEs will be reported in the subject's medical record and respective section of the eCRF (requirements for screen failures see [Section 12.1](#)).

Unsolicited AEs will be assessed and documented from ICF signature through EAP, and if ongoing at that time followed until resolution or until the subject's last trial visit, at the latest. SAEs and AESIs will be collected through the end of the trial, including during the FU period.

SAEs and AESIs will be assessed and documented at all trial visits. (S)AEs would only be considered as AESIs once subject has received first vaccination. SAEs and AESIs will be followed-up until resolution or achievement of stable clinical conditions.

Assessment of Intensity

For all unsolicited AEs not represented in the Toxicity Grading Scale for Healthy Adult and Adolescent Volunteers Enrolled in Preventive Vaccine Clinical Trials ([FDA, 2007](#)), the maximum intensity will be based on the following descriptions:

- Grade 1** An AE which is easily tolerated by the subject, causing minimal discomfort and not interfering with daily activities.
- Grade 2** An AE which is sufficiently discomforting to interfere with daily activities, but does not require medical intervention (non-narcotic pain reliever or other nonprescription medication are not considered “medical intervention” for this purpose).
- Grade 3** An AE which prevents daily activities and which requires medical intervention (non-narcotic pain reliever or other nonprescription medication are not considered “medical intervention” for this purpose)
- Grade 4** Life-threatening, or disabling.

Assessment of Causality

The relationship between the occurrence of an AE and the IMP will be assessed using the categories presented below. For expedited reporting and all other purposes, the categories “none” and “unlikely” will represent no evidence or argument to suggest a causal relationship, while “possible”, “probable” and “definite” will be seen to convey that there is evidence or argument to suggest a causal relationship. To ensure reporting, all AEs without a causality assessment from the investigator will preliminarily be classified as “possible”.

In terms of binary causality assessments unlikely and not related in clinical trials is lumped to “not related” whereas other causality assessments as per below are lumped to “related”.

- Not related** The time interval between administration of the IMP and the occurrence or worsening of the AE rules out a relationship, and/or alternative cause is established and there is no evidence of a (concomitant) causal connection with or worsening caused by the IMP.

Unlikely	The time interval between administration of the IMP and the occurrence or worsening of the AE makes a causal relationship unlikely, and/or the known effects of the IMP or substance class provide no indication of a (concomitant) causal connection with or worsening caused by the IMP and there is another cause which serves as an adequate explanation, and/or although the known effects of the IMP or substance class make it possible to derive a plausible causal chain with regard to a (concomitant) causal connection or worsening, however, another cause is considerably more likely, and/or another cause of the AE has been identified and a (concomitant) causal connection with or worsening caused by the IMP is unlikely.
Possible	A plausible causal chain with regard to a (concomitant) causal connection with / worsening of the AE can be derived from the pharmacological properties of the IMP or substance class. However, other approximately equally likely causes are known, or although the pharmacological properties of the IMP or substance class provide no indication of a (concomitant) causal connection with / worsening of the AE, there is no other known cause which provides an adequate explanation.
Probable	The pharmacological properties of the IMP or substance class, and/or the course of the AE after discontinuation of the IMP and possible subsequent re-exposure, and/or specific findings (e.g., positive allergy test or antibodies against the IMP / metabolites) suggest a (concomitant) causal connection with / worsening of the AE resulting from the IMP, however another cause cannot completely be ruled out.
Definite	The pharmacological properties of the IMP or substance class and/or the course of the AE after discontinuation of the IMP and possible subsequent re-exposure, and/or specific findings (e.g., positive allergy test or antibodies against the IMP / metabolites) definitely indicate that there is a (concomitant) causal connection with / worsening of the AE resulting from the IMP and there are no indications of other causes.

8.13 Solicited AEs

After the vaccination, subjects receive a memory aid to record solicited local and general AEs most likely to occur on the day of vaccination and the following 7 days (Days 1 to 8 following vaccination, 8-day period).

All solicited symptoms observed after vaccination with details concerning the intensity and the course of the symptom should be documented in the memory aid. The CTS will collect the memory aid at the following visit, review the memory aid with the subject, and transfer the results to the eCRF and the subject's medical record. The investigator's assessment of the symptoms will also be recorded in the eCRF including causality (for solicited general AEs),

seriousness, outcome, action taken with vaccine, and any intervention required. Local and general symptoms still ongoing after 8 days will continue to be measured and documented each day until resolved.

To standardize procedures uniform rulers will be handed out to subjects for measurements of erythema, swelling and induration diameters, as will digital thermometers for oral measurements of body temperature.

In case of severe and unexpected local and/or general reactions, the subject should be instructed to contact the trial physician outside of scheduled trial visits.

8.14 Solicited Local AEs

The solicited local symptoms erythema, swelling, induration, pruritus and pain at the injection site are to be documented in the memory aid by the subjects.

Assessment of Intensity

Injection site erythema, swelling, and induration will be assessed based on the longest diameter as measured by the subject in mm and recorded in the memory aid. Subjects are asked to document the solicited local AEs in the memory aid as described in [Table 2](#) below.

Table 2 Grading of Local Symptoms from the Subject's Memory Aid

MedDRA coded Preferred Term Local Adverse Events	Grade	Severity
Injection site erythema, Injection site swelling, and Injection site induration (longest diameter measured in mm)	0	0 mm
	1	<30 mm
	2	≥30 – <100 mm
	3	≥100 mm
Injection site pruritis	0	Absent
	1	Mild
	2	Moderate
	3	Severe
Injection site pain	0	Absent
	1	Painful on touch
	2	Painful when limb is moved
	3	Spontaneously painful/prevents normal activity

Assessment of Causality

Solicited local AEs are defined as being related to the vaccine.

8.15 Solicited General AEs

The solicited general symptoms body temperature, headache, myalgia, nausea, chills and fatigue are to be documented in the memory aid by the subjects.

Assessment of Intensity

Subjects are asked to document the solicited general AEs in the memory aid as described in [Table 3](#) below. In the subject's memory aid, the grading of symptom intensity is described in basic, easily understood language based on the following descriptions:

Table 3 Grading of General Symptoms from the Subject's Memory Aid

MedDRA coded Preferred Term General Adverse Events	Grade	Severity
Body temperature (oral) *	0	<37.5°C (<99.5°F)
	1	≥37.5 – <38.0°C (≥99.5 – <100.4°F)
	2	≥38.0 – <39.0°C (≥100.4 – <102.2°F)
	3	≥39.0 – <40.0°C (≥102.2 – <104.0°F)
	4	≥40.0°C (≥104.0°F)
Headache, Myalgia, Nausea, Chills and Fatigue	0	None
	1	Mild: easily tolerated, minimal discomfort and no interference with daily activity
	2	Moderate: Some interference with daily activity
	3	Severe: Prevents daily activity

*Pyrexia is defined as oral temperature ≥38.0°C (≥100.4°F)

Assessment of Causality

Causal relationship between solicited general AEs and the vaccine will be assessed by the investigator using the same categories as for unsolicited AEs (see [Section 8.12](#)).

8.16 Safety Laboratory Measurements

The intensity of laboratory/systemic toxicities measured quantitatively will be graded according to the [Toxicity Grading Scale for Healthy Adult and Adolescent Volunteers Enrolled in Preventive Vaccine Clinical Trials \(FDA, 2007\)](#). The laboratory values provided in this toxicity grading scale serve as guidelines and are dependent upon institutional parameters. Institutional specific toxicity gradings will be included in site specific manuals as needed.

Safety laboratory is determined at SCR and V3 (one-dose vaccination schedule) or at SCR, V3 and V6 (two-dose vaccination schedule) and at any other visit(s) if clinically indicated. If the safety laboratory measurements are performed at a local laboratory, the laboratory normal ranges are provided by the safety laboratory and are filed in the Investigator File. Safety laboratory parameters to be evaluated are:

Hematology:

Red blood cell count, hemoglobin, total and differential White Blood Cell count (WBC), platelet count, Hematocrit, mean corpuscular/cell volume (MCV), mean corpuscular/cellular hemoglobin (MCH), mean corpuscular hemoglobin concentration (MCHC) and red blood cell distribution width (RDW) are routinely performed as part of the complete blood cell count and will be included in the laboratory report.

Serum chemistry:

Total bilirubin, Alkaline Phosphatase (AP), Aspartate Aminotransferase (AST), Alanine Aminotransferase (ALT), serum creatinine, sodium, potassium, calcium, CRP.

Pregnancy test:

A β -human choriogonadotropin (β -HCG) pregnancy test will be conducted for all WOCBP at SCR and prior to each vaccination V1 (one-dose vaccination schedule) or V1 and V4 (two-dose vaccination schedule). At SCR a serum β -HCG pregnancy test will be performed; all other pregnancy tests will be conducted as urine β -HCG tests.

Virology:

The following parameters will only be evaluated during the screening period for assessment of inclusion/exclusion criteria:

Human immunodeficiency virus antibody test (anti-HIV)

HBsAG

HCV

Severe Acute Respiratory Syndrome Coronavirus 2 Testing:

SARS-CoV-2 specific antibody test (at SCR only)

SARS-CoV-2 infection test (according to trial schedule)

8.17 Cardiac Assessment

Electrocardiogram (ECG):

A standard 12-lead ECG will be taken at the SCR. At any other visit an ECG is only performed if clinically indicated. For unclear ECGs the investigator can obtain ECG over-read by a local cardiologist.

The investigator will assess the clinical significance for abnormal ECGs. Interpretation support for SCR ECGs is provided in [Appendix 3: Interpretation Support for Assessment of SCR ECGs](#).

8.18 Pregnancy

As per inclusion criteria, WOCBP must have a negative serum pregnancy test at SCR and a negative urine pregnancy test within 24 hours prior to each vaccination. In addition, they must have used an acceptable method of contraception for 30 days prior to the first vaccination, must agree to use an acceptable method of contraception during the trial, and must avoid becoming pregnant for at least 30 days after the last vaccination. Nevertheless, IMP exposed pregnancies cannot be excluded with certainty. Subjects who become pregnant prior to the first vaccination will be excluded from the trial and are regarded as SCR failure. Subjects who become pregnant during the active trial phase (up to and including 1 month [minimum 28 days] after receiving a dose of vaccine) must not receive additional doses of vaccine but may continue other trial procedures at the discretion of the investigator (see [Section 4.7](#)). All reports, where the embryo or fetus may have been exposed to the IMP (through maternal exposure) will be followed-up until delivery to collect information on the outcome of the pregnancy (see [Section 8.21](#)).

Subjects will be instructed to notify the investigator if it is determined (also after completion of the trial) that they became pregnant either during the trial or within 1 month (minimum 28 days) after receiving the last vaccine dose.

8.19 Reporting

8.20 Reporting of SAE and AESI

All SAEs (collection starts at signing of ICF) and AESIs (collection starts upon receiving first vaccination) occurring throughout the entire course of the trial have to be entered in the eCRF within 24 hours of awareness by the investigators, which triggers an autogenerated output to the Drug Safety (DS)/PV Department of the contract research organization (CRO).

In case the eCRF is unavailable, the SAE and AESI report form is sent via email to the DS/PV Department of the CRO within 24 hours of becoming aware of the SAE or AESI.

Serious adverse events and AESIs should be sent to:

[REDACTED]

[figure not shown]
Cc: [REDACTED]

The investigator should not delay reporting because of missing information. Nonetheless, the report should be as complete as possible. This initial notification should include, as a minimum, sufficient information to permit identification of the following:

- the reporter (investigator's name and contact information)
- the subject
- involved trial medication
- AE(s)
- seriousness criterion
- date of onset

BN/CRO is responsible for expedited as well as periodic reporting to the involved regulatory authorities according to applicable laws and guidelines, and for forwarding final safety reports to the clinical CRO.

Regulatory authorities will be notified as soon as possible but no later than 7 days after first knowledge of fatal or life-threatening unexpected SAE with an at least possible relationship to the IMP (serious adverse drug reaction [SADR]) and no later than 15 days after knowledge of any other unexpected SADR. The same process applies for AESIs. The clinical CRO is responsible for reporting to the Ethics Committees or IRBs and HRPO. [Figure 2](#) outlines the reporting process and timelines for SAEs and AESIs.

Figure 2**Algorithm for Reporting of SAEs and AESIs**

8.21 Reporting of Pregnancies

If a subject becomes pregnant during the active trial phase (up to and including 1 month [minimum 28 days] after receiving the trial vaccination) this must be recorded on the Pregnancy eCRF (or Pregnancy Notification Report Form if EDC unavailable) within 24 hours of the investigator becoming aware of the event ([Section 8.20](#)).

A pregnancy will be followed to term, any premature terminations reported, and the health status of the mother and child including date of delivery and the child's sex and weight will be reported by the investigator to the CRO DS and BN as soon as possible after delivery by recording outcome on the pregnancy eCRF (or Pregnancy Outcome Report Form if EDC unavailable).

Any event during pregnancy fulfilling the criteria for an SAE or AESI will be reported to the CRO DS/PV department (see [Section 8.20](#)). However, hospitalization for delivery is a prospectively planned hospitalization and is not considered a SAE, *per se*.

9 Statistical Considerations

9.1 Randomization Procedure

No randomization procedure will be used for this trial. Recruitment will be performed with a run-in period including enrollment of 6 subjects into Group 1 and 2 (3 subjects in each). Subjects will be vaccinated in a consecutive manner as described in [Section 4.1](#). After completion of V2 and positive review of safety data by the DMC, the DMC will allow for the enrollment of all remaining subjects. Assignment into Group 1 versus Group 2 and 3 will be based on the subjects' baseline SARS-CoV-2 antibody status. For seropositive subjects the reason for seropositivity will be documented: previous COVID-19 infection, mRNA vaccinated, adenovirus-vaccinated, or a mix of those.

Due to the timing of the addition of Group 3, enrollment into Group 2 will be completed prior to enrolling subjects into Group 3. Therefore, no randomization will be required for the seropositive subjects.

9.2 Sample Size Calculation

Group 1: Up to 30 subjects determined to be seronegative for SARS-CoV-2 antibodies at SCR will be enrolled in Group 1.

Group 2: approximately 90 subjects determined to be seropositive for SARS-CoV-2 antibodies at SCR will be enrolled in Group 2.

Group 3: approximately 90 subjects determined to be seropositive for SARS-CoV-2 antibodies at SCR will be enrolled in Group 3.

The primary objective of Group 1 is to estimate the level of neutralizing antibodies 2 weeks after the second vaccination. This will be measured by the geometric mean of the neutralizing antibody titers and its 95% confidence interval. Based on published data on the peak neutralizing antibody titers following vaccination with licensed SARS-CoV-2 vaccines, we assume the standard deviation in logarithm 10 (\log_{10}) scale will be approximately 0.5. When the sample size is 30, a two-sided 95% confidence interval will extend 0.179 from the observed mean in \log_{10} scale. The corresponding 95% confidence interval for the geometric mean will be between 132 and 302 if the point estimate is 200; it will be between 166 and 377 if the point estimate is 250. The lower bound of 132 to 166 is in the similar range of licensed SARS-CoV-2 vaccines ([Jin et al., 2021](#)).

The primary objective for Groups 2 and 3 is to estimate the geometric mean of the ratio of neutralizing antibody titers 2 weeks after the single booster vaccination with ABNCoV2 versus the pre-booster level. We assume the same standard deviation of 0.5 in \log_{10} scale in both pre-booster and post-booster titers; the correlation coefficient between the pre-booster and post-booster titers is 0.3; and the distribution of the ratio is log-normal. When the sample size is 90, a two-sided 95% confidence interval will extend 0.122 from the observed mean in \log_{10} difference. If the observed geometric mean of the ratio is 4 (i.e., a 4-fold increase after booster), the 95% confidence interval will be (3.0, 5.3). When stratified by baseline titer subgroups (<median or \geq median), the lower bound of the 95% confidence interval will be at least 2.7 when the observed ratio is 4 with a subgroup size of 45.

9.3 Multiplicity

Since there is no hypothesis test in this phase 2 trial, multiplicity is not applicable.

9.4 Variables

Please refer to endpoints in Protocol Synopsis [Section 1.3](#).

9.5 Analysis Population

The analysis population includes subjects who meet all of the inclusion and none of the exclusion criteria as defined separately for the three groups in [Section 1.3](#), e.g., subjects assigned to Group 1 must be confirmed seronegative; subjects assigned to Groups 2 and 3 must be confirmed seropositive.

The Safety Analysis Set for all safety variables and population level summaries includes all subjects who received at least 1 dose of the ABNCoV2 vaccine.

The Immunogenicity Analysis Set for immunogenicity variables and population level summaries includes all subjects who are in the Safety Analysis Set and have at least 1 post-vaccination neutralizing antibody titer result. A data review meeting will determine if any protocol violations will affect the immunogenicity outcomes and these subjects will be removed from the analysis set.

9.6 Analysis Methods

9.7 Primary Estimand

9.8 Population Level Summary

Group 1: Geometric mean of SARS-CoV-2 neutralizing antibody titers at 2 weeks after the boost vaccination.

Groups 2 and 3: Geometric mean of the fold-increases, defined as the ratio of SARS-CoV-2 neutralizing antibody titer at 2 weeks divided by the neutralizing antibody titer at baseline (last measurement prior to ABNCoV2 vaccination).

9.9 Intercurrent Events

The following are considered intercurrent events: 1) development of COVID-19 symptoms prior to 2 weeks after the last vaccination (Week 6 in Group 1 and Week 2 in Groups 2 and 3) and having a positive test for SARS-CoV-2 infection, and 2) discontinuation due to AEs from either the second vaccination (Group 1) or the trial. For the primary estimand, the second intercurrent event is not considered as having an impact on the SARS-CoV-2 neutralizing antibody levels and therefore the “treatment policy” strategy will be used. Subjects who come in contact with the virus can have significant interference with the SARS-CoV-2 neutralizing antibody levels and thus will be excluded from the primary analysis. This is equivalent to the “while on treatment” strategy.

9.10 Primary Analysis

The geometric mean of SARS-CoV-2 neutralizing antibody titers (Group 1) and fold increases (Groups 2 and 3) 2 weeks after the last vaccination will be summarized along with their 95% confidence intervals. The arithmetic means and the corresponding 95% confidence intervals on the \log_{10} scale will be calculated using the normal approximation approach. The geometric means and the 95% confidence intervals will be obtained by exponentiating the \log_{10} means and confidence limits. For Groups 2 and 3, analyses of fold-increases will be performed by baseline titer categories ($<\text{median}$ or $\geq\text{median}$) to account for the expected variation in the baseline neutralizing titer due to the different reasons for seropositivity (i.e., previous mRNA vaccination, previous Adenovirus-based vaccination, or previous COVID-19 infection). As the Groups 2 and

3 baseline titer distributions are assumed to be the same, the median baseline neutralizing titer category will be derived from the median of both groups. This will allow for comparability between the geometric fold-increases by dose level (i.e., 100 µg vs. 50 µg).

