9.11 Sensitivity and Supportive Analyses

The primary analysis will be supported by descriptive summaries (geometric means, 95% confidence intervals of the geometric means and median) for each time point (pre- and post-vaccination). Response rates, with response being defined as SARS-CoV-2 neutralizing antibody titers above the limit of quantification in Group 1, or having an at least 2-fold or 4-fold increase from baseline in Groups 2 and 3, respectively, will also be summarized and corresponding 95% confidence intervals will be calculated using the Clopper-Pearson method. For these analyses, both the median categories will be used as defined for the primary analysis as well as quartile categories from the pooled Group 2 and 3 baseline neutralizing titer data.

Because the window between vaccination and the primary endpoint measurement is short, the number of subjects with missing data due to the intercurrent event is expected to be small. If there are any, missing data will be imputed using the multiple imputation method as a sensitivity analysis.

The primary analyses will also be performed by age groups as supportive analyses: 18 to <50 years, 50 to <65 years, 65 to <75 years, and ≥ 75 years.

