4.2.2 Main Analytical Approach

The estimate of the primary estimand will be created using the Immunogenicity Analysis Set, which will include only subjects who have no protocol deviations that will substantially affect the immunogenicity outcomes. Due to this, missing values for the primary estimand analysis are unexpected. Subjects who have a value for the primary time point but developed COVID-19 symptoms prior to 2 weeks after the last vaccination, and had a positive PCR result for SARS-CoV-2 infection prior to the 2 weeks after the last vaccination time point, will be excluded from the analysis due to the interference the infection will have on the resulting neutralizing antibody results.

The geometric mean of SARS-CoV-2 neutralizing antibody titers (Group 1), and fold increases (Groups 2 and 3) 2 weeks after the last vaccination, will be summarized along with their 95% CIs. No statistical hypothesis testing will be performed for this single arm trial.

Geometric mean titers (GMTs) will be obtained by computing the arithmetic means and the corresponding 95% CIs on the \log_{10} scale, and then exponentiating the \log_{10} means and confidence limits to return the results to the original scale.

Fold increases for Groups 2 and 3 will be calculated as the ratio of the SARS-CoV-2 neutralizing antibody titer at 2 weeks post-last vaccination to the baseline neutralizing antibody titer (i.e., last measurement prior to vaccination). Geometric mean fold increases (GMFIs) will be calculated in the same manner as GMTs.

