4.7 Changes to Protocol-planned Analyses

The primary analysis has been updated to include only Groups 2 and 3 through the end of the Active Trial Period to assist in planning for the Phase 3 trial.

For neutralizing titer response in seropositive subjects, a threshold of ≥ 6 -fold increase has been added to the response summaries.

5 Subject Population Summaries

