5.1.1.6 Prior and Concomitant Medication

Displays of **prior** medications include medications where end date is before date of first administration of trial vaccine. Displays of **concomitant** medications include all ongoing medications, medications with missing end dates, or medications with end date after the first administration of trial vaccination. Tables by ATC Level 2 class and preferred name will be

presented for the Safety Analysis Spet. If ATC Level 2 class is not available, the next highest class available will be used. Subject level listings will be created by group, subject, ATC Level 2 class, preferred name, and verbatim term.

6 Sample Size Determination

Group 1: approximately 30 subjects determined to be seronegative for SARS-CoV-2 antibodies at screening will be enrolled in Group 1, 100 μ g dose.

Group 2: approximately 90 subjects determined to be seropositive for SARS-CoV-2 antibodies at screening will be enrolled in Group 2, 100 μ g dose.

Group 3: approximately 90 subjects determined to be seropositive for SARS-CoV-2 antibodies at screening will be enrolled in Group 3, 50 μ g dose.

The primary objective of Group 1 is to estimate the level of neutralizing antibodies 2 weeks after the last (i.e., second) vaccination. This will be measured by the geometric mean of the neutralizing antibody titers and its 95% CI. Based on published data on the peak neutralizing antibody titers following vaccination with licensed SARS-CoV-2 vaccines, we assume the SD in logarithm 10 (\log_{10}) scale will be approximately 0.5. When the sample size is 30, a two-sided 95% CI will extend 0.179 from the observed mean in \log_{10} scale. The corresponding 95% CI for the geometric mean will be between 132 and 302 if the point estimate is 200; it will be between 166 and 377 if the point estimate is 250. The lower bound of 132 to 166 is in the similar range of licensed SARS-CoV-2 vaccines ([Jin et al., 2021](#)).

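### The protocol's normal-approximation intervals on the log10 scale ignore that the SD is estimated: the effect is negligible at n=90, slight at n=30 and material only in small Group 1 age cells

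*Protocol*

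**What the plan says.** Protocol 9.10 obtains geometric means and their limits by back-transforming log10 means and 95% intervals, and says these "will be calculated using the normal approximation approach". The rule covers Group 1 titers and Groups 2 and 3 fold-increases.

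SAP 4.2.2 describes the same calculation as "computing the arithmetic means and the corresponding 95% CIs on the" log10 scale, followed by back-transformation. It mentions neither a normal approximation nor a t distribution. The SAP's introduction sends changes from the protocol's analyses to SAP 4.7. That section lists two, neither about the interval method: "The primary analysis has been updated to include only Groups 2 and 3 through the end of the Active Trial Period", and an added 6-fold response threshold.

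On planned precision, protocol 9.2 takes an SD that on the log10 "scale will be approximately 0.5" and concludes: "When the sample size is 30, a two-sided 95% confidence interval will extend 0.179 from the observed mean". SAP section 6 repeats this: "a two-sided 95% CI will extend 0.179 from the observed mean".

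On subgroups, protocol 9.11 adds: "The primary analyses will also be performed by age groups as supportive analyses", with four age categories. SAP 4.2.4 keeps these and adds sex. Neither document gives subgroup sizes or a small-sample rule for the intervals.

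**The concern.** A normal multiplier is exact when the SD is known. Here the SD is known only in the planning calculation; every reported interval will use the sample SD. SAP 4.2.1 assumes log-normal titers, and protocol 9.2 assumes a log-normal ratio. Under those assumptions the t interval has exactly 95% coverage and the z interval has less, with the gap growing as n falls.

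The trial tests no hypothesis, so the interval around each geometric mean is how the uncertainty of the primary result is conveyed. For proportions the plan uses the exact Clopper-Pearson method, and it gives no reason for a large-sample approximation for the means. The practical risk is that the age-group tables, where cells can be very small, show intervals labelled 95% that are noticeably too narrow.

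**Working it through.** **Inputs.** From protocol 9.2 and SAP section 6: log10 SD 0.5; n=30 (Group 1), 90 (Groups 2 and 3 each) and 45 (baseline-titer subgroup); pre/post correlation 0.3. From protocol 9.11: four age categories.

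**Formulas.** Half-width h = m × SD/√n, with limits GM × 10^(±h). The multiplier m is 1.960 for z or t(0.975, n-1). Actual coverage of a nominal 95% z interval with an estimated SD is 2·T(1.96; n-1) − 1, where T is the t distribution function.

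**Step 1: reproduce the plan's Group 1 figures.** 1.960 × 0.5/√30 = 0.1789. At 200 the limits are 132.5 and 302.0; at 250 they are 165.6 and 377.4. These match the stated 0.179, 132 to 302 and 166 to 377, so the planning figures used z.

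**Step 2: Group 1 with t.** t(0.975, 29) = 2.045, so h = 2.045 × 0.5/√30 = 0.1867. The limits become 130 to 307 at 200, and 163 to 384 at 250. The half-width is about 4% larger.

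**Step 3: Groups 2 and 3.** SD of the log10 difference = √(0.25 + 0.25 − 2 × 0.3 × 0.25) = 0.5916.

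- n=90, z: h = 0.1222, limits 3.02 to 5.30, matching the stated 0.122 and (3.0, 5.3).
- n=90, t (1.987): h = 0.1239, limits 3.01 to 5.32, still (3.0, 5.3) to one decimal.
- n=45, z: h = 0.1729, lower limit 2.69. With t (2.015): h = 0.1777, lower limit 2.66.

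**Step 4: coverage by sample size.**

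| n | Coverage of z interval | t width / z width (log10) |
|---|---|---|
| 90 | 94.7% | 1.01 |
| 45 | 94.4% | 1.03 |
| 30 | 94.0% | 1.04 |
| 22 | 93.7% | 1.06 |
| 10 | 91.8% | 1.15 |
| 7 | 90.2% | 1.25 |
| 5 | 87.8% | 1.42 |

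**Step 5: which small cells must occur.** In Group 1, 30/4 = 7.5, so at least one age cell has 7 or fewer subjects. In Groups 2 and 3, 90/4 = 22.5, so each has at least one age cell with 22 or fewer. The documents give no cell sizes, so the rows for n=10 and n=5 are illustrative.

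**Step 6: what this looks like at n=7** (SD 0.5, geometric mean 200). With z: h = 0.370, limits 85 to 469. With t (2.447): h = 0.462, limits 69 to 580.

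**The case against.** Several points on the other side stand.

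- The SAP governs the programming and names no multiplier, so a t interval would already comply with SAP 4.2.2. A reader might infer from the 0.179 that the final analysis is bound to use z. The documents do not show that: 0.179 is a planning figure with an assumed SD, for which z is a natural choice. What remains is the protocol's wording, which most naturally means z and which the SAP does not replace. If t is programmed, the analysis departs from that wording without an entry in SAP 4.7.
- SAP 4.6 and 4.7 limit the primary analysis that informs phase 3 to Groups 2 and 3, where z and t barely differ. A reader might infer that this analysis is compromised; at n=90 the stated (3.0, 5.3) is unchanged.
- At n=30 the effect is smaller than the uncertainty in the inputs. An SD of 0.522 with z also gives 1.960 × 0.522/√30 = 0.187.
- A reader might set 2.66 against the stated lower bound of at least 2.7 at n=45 and blame the z multiplier. With z the bound is 2.69, also just under 2.7, and both round to 2.7. That is rounding.
- A reader might call the geometric-mean intervals the trial's only inferential output. They are not: Clopper-Pearson intervals (protocol 9.11 and 9.15; SAP 4.2.4 and 4.3.1.2) and a Pearson correlation with interval and p-value (SAP 4.4) are also planned.
- The age analyses are supportive, and at n=7 even the t interval is too wide to be very informative. That limits the consequence, but it does not justify labelling a roughly 90% interval as 95%.

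**Conclusion.** The point holds at low severity. Followed as written, protocol 9.10 gives intervals that fall short of 95% coverage whenever the SD is estimated, and the SAP neither confirms nor replaces that rule. The shortfall is 0.3 percentage points at n=90 and 1.0 at n=30. It is about 5 points or more in at least one Group 1 age cell, provided that cell has enough subjects for an interval at all. No sample size, estimand or design conclusion changes.

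The coverage figures assume normally distributed log10 values. SAP 4.1 replaces results below the detection and quantitation limits with half-limits, so the distribution will not be exactly normal and the percentages are approximate. The bound of 7 subjects assumes about 30 in Group 1 (it holds for any total up to 31); exclusions from the Immunogenicity Analysis Set would only reduce the cells. The widths at n=7 assume the planning SD of 0.5 applies within the cell.

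**What to change.** In protocol 9.10 and SAP 4.2.2, state that log10-scale intervals use the t distribution with n-1 degrees of freedom in all groups and subgroups. Record this in SAP 4.7 as a change from the protocol's interval method.

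In protocol 9.2 and SAP section 6, restate:

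- the Group 1 half-width as 0.187, with 130 to 307 at 200 and 163 to 384 at 250;
- the Groups 2 and 3 half-width as 0.124, leaving (3.0, 5.3) as it is;
- the bound for a subgroup of 45, if edited at all, as approximately 2.7 instead of at least 2.7.

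The cost is one sentence in each document, one entry in SAP 4.7 and a few slightly less favourable planning figures. No extra subjects or data are needed.
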